11.1.6 Physical examination

Results from physical examinations will be recorded in the CRF. Clinically significant changes from baseline that meet the definition of an AE will be recorded on the AE form. Study day, date, body system, status (normal, abnormal or not examined), and specification (if abnormal) will be listed. Numbers and percentages of subjects with abnormal findings for each body system will be summarized.

11.1.7 Murine antigens skin test

Results from murine antigens skin testing will be recorded in the CRF. Study day and test result will be listed.

11.1.8 Murine leukemia virus

Results from murine leukemia virus testing will be recorded in a separate spreadsheet. Study day and test result will be listed.

12 MISCELLANEOUS DATA COLLECTION

12.1 Subject Progress

A listing of subject progress through the study will be provided that shows visits completed and dates of each visit.

13 STATEMENT OF COMPLIANCE

This analysis will be conducted in full compliance with the analysis plan, the study protocol (as applicable), and all applicable U.S. Food and Drug Administration regulations. This SAP supersedes any statistical considerations identified in the study protocol. Any differences between this statistical analysis plan and the study protocol will be presented and explained in the CSR.

14 SOFTWARE

Tables, listings, figures, and analyses will be produced using SAS® Version 9.1.3 or higher (SAS Institute Inc., Cary, NC), Microsoft® Excel version 2007 or higher (Microsoft Corp., Redmond, WA).

16 APPENDICES

16.1 Listings

Listing #	Listings
16.2.1.1	Subject disposition
16.2.1.2.1	Subject progress through study, 1 st implant
16.2.1.2.2	Subject progress through study, 2 nd implant
16.2.1.2.3	Subject progress through study, 3 rd implant
16.2.1.2.4	Subject progress through study, 4 th implant
16.2.2.1	Inclusion
16.2.2.2	Exclusion
16.2.3	Eligibility
16.2.4.1	Baseline characteristics
16.2.4.2	Contraception methods
16.2.4.3	Medical history
16.2.4.4.1	Primary oncology diagnosis
16.2.4.4.2	Previous oncology diagnosis
16.2.4.7.1	Pre-treatment medications
16.2.4.7.2	Con meds
16.2.5	Implantation
16.2.6.1.1	Global Clinical Assessment
16.2.6.1.2	Activities of Daily Living
16.2.6.1.3	Quality of Life Scale
16.2.6.1.4	Pain Scale Assessment
16.2.6.1.5	ECOG
16.2.6.2.1	Tumor markers
16.2.6.2.2	Cytokines
16.2.6.3	Tumor size and state
16.2.6.4.1	Overall survival (from T ₀)
16.2.6.4.2	Time from first implantation to radiologically evident disease progression
16.2.6.5.1.1	Time from first implantation to death
16.2.6.5.1.2	Time from diagnosis of Stage IV disease to death
16.2.7.1.1	AEs
16.2.7.1.2	AE comments

Listing #	Listings
16.2.7.2	SAEs
16.2.7.3.1	Treatment-emergent AEs resulting in discontinuation
16.2.7.3.2	Treatment-emergent AEs resulting in death
16.2.8.1	Laboratory testing data collection
16.2.8.2.1.1	Serum chemistry toxicity grades
16.2.8.2.1.2	Serum chemistry
16.2.8.2.2.1	Hematology toxicity grades
16.2.8.2.2.2	Hematology
16.2.8.2.3.1	Immunophenotyping toxicity grades
16.2.8.2.3.2	Immunophenotyping
16.2.8.2.X	Other labs
16.2.8.3	Comments
16.2.8.4	Labs reported as AEs and/or with toxicity Grade ≥ 3
16.2.9.1	Physical exam
16.2.9.2	Neuro exam details
16.2.9.3	Visit reviews
16.2.9.4.1	Vital signs
16.2.9.4.2	Home care log vital signs
16.2.9.5	ECG
16.2.9.6	Wound check
16.2.9.7	Mouse antigen skin tests
16.2.9.8	Murine virus
16.2.9.9.1	Chest x-ray
16.2.9.9.2	CT / PET / MRI scans
16.2.9.9.3	Rad disease assessments done
16.2.9.10	Hospitalizations
16.2.9.11	Comments
16.2.9.12	PI signatures

16.2 Tables

Table #	Tables
14.1.1.1	Completion / withdrawal
14.1.1.2.1	Subject disposition, 1 implant
14.1.1.2.2	Subject disposition, 2 implants
14.1.1.2.3	Subject disposition, 3 implants
14.1.1.2.4	Subject disposition, 4 implants
14.1.2.1	Baseline characteristics
14.1.2.2	Contraception methods
14.1.2.3.1	Presenting oncology diagnosis
14.1.2.3.2	Previous oncology diagnosis
14.1.3	Con meds by drug class and preferred name
14.1.4	Number of Implantations and number of macrobeads implanted
14.2.1.1	Global Clinical Assessment
14.2.1.2	Activities of Daily Living
14.2.1.3	Quality of Life Scale (imputed)
14.2.1.3X	Quality of Life Scale (not imputed)
14.2.1.4.1	Pain Scale Assessment, Pain Level
14.2.1.4.2	Pain Location
14.2.1.5	ECOG
14.2.2.1	Tumor markers
14.2.2.2	Cytokines
14.2.3	Tumor size and state
14.2.4	Overall survival (from the most recent radiological scan showing evident disease progression to death)
14.2.5	Time from first implantation to death
14.2.6	Time from diagnosis of Stage IV disease to death
14.3.1.1.1	AE summary
14.3.1.1.2	Death summary
14.3.1.2	Treatment-emergent AEs by SOC
14.3.1.3.1	Treatment-emergent AEs by SOC and preferred term
14.3.1.3.2	Treatment-emergent AEs by severity
14.3.1.3.3	Treatment-emergent AEs by relationship
14.3.1.6	Treatment-emergent frequently reported ($\geq 2\%$ in all patients combined) AEs
14.3.2	Treatment-emergent SAEs by severity
14.3.4.1.1	Serum Chemistry Observed & Changes

Table #	Tables
14.3.4.1.2	Serum Chemistry, out of range flags
14.3.4.1.3	Serum Chemistry, Shift Table
14.3.4.1.4	Serum Chemistry Toxicity Grades
14.3.4.2.1	Hematology Observed & Changes
14.3.4.2.2	Hematology, out of range flag
14.3.4.2.3	Hematology, Shift Table
14.3.4.2.4	Hematology Toxicity Grades
14.3.5.1	Physical exam
14.3.6.1	Vital signs
14.3.6.2	Vital signs from diary
14.3.7	ECG

Mortality Figures	
16.2.6.4.1	Overall survival (from the most recent radiological scan showing progression)
16.2.6.5.1.1	Time from first implantation to death
16.2.6.5.1.2	Time from diagnosis of Stage IV disease to death

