End of Study	When all patients have died or have been lost to follow-up, whichever occurs first
Enrolled Patients	Eligible patients who have signed an Informed Consent Form (ICF)
Sponsor	The Rogosin Institute
Time of origin (T_0)	Date of the first scan showing disease progression after completion of prior treatment. Scan must be prior to first implant. Used for mortality analyses only.
Treated Population	Patients who received at least one implant
Treatment-Emergent Adverse Event (TEAE)	An adverse event which occurred during or after the first implantation and up to 120 days after the last implantation

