3.3 Study Outcomes

3.3.1 Efficacy

The primary efficacy outcome is post-implantation all-cause mortality, where time to death is defined as the time from the first scan showing disease progression after completion of prior treatment (time of origin, T_0) to death from any cause.

Secondary efficacy outcomes are (if feasible):

- Time from first implantation to death.
- Time from disease Stage IV diagnosis to death.
- Changes from baseline based on Magnetic Resonance Imaging (MRI), computerized tomography (CT) or positron emission tomography (PET)-CT scan, and other appropriate imaging techniques (e.g., sonography, bone scans, other x-rays) as indicated, if feasible.
 - In primary and/or secondary tumor size (volume, area) and
 - In state (necrosis, vascularization) on MRI, CT or PET-CT scan, and other appropriate imaging techniques (e.g., sonography, bone scans, other x-rays) as indicated.
- Change from baseline in tumor markers (CEA, CA19-9)
- Changes from baseline in CA125 (as a marker of inflammation)
- Changes from baseline in
 - Clinician Global Clinical Assessment
 - Activities of daily living
 - Symptom rating
 - Quality of life (QCQ-C30)
 - Pain scale
 - ECOG
- Additional exploratory efficacy outcomes may be analyzed if feasible and will be defined in the CSR.

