6.4 Visit Windows

6.4.1 Study time points

The following study time points are critical in terms of screening procedures, implantation and study termination. Study time point labels correspond to those that are used in the protocol (minus visit numbers) and that will be used in listings and tables. A complete description of all study time points is contained in the Schedule of Assessments ([Section 4](#)). Study visit labels in the Schedule of Assessments differ somewhat from those that are used in the text of the protocol and in the SAP (see samples below):

SAP	Text of Protocol	Schedule of Assessments
Implant 2 / Day 0	Visit 6 / Implant 2 / Day 0	Visit 6 / Implant 2
Implant 3 / Day 0	Visit 11 / Implant 3 / Day 0	Visit 11 / Implant 3
Implant 4 / Day 0	Visit 16 / Implant 4 / Day 0	Visit 16 / Implant 4

In the time-to-death analyses, the time of origin (T_0) will be defined separately for each analysis:

- Time from first scan showing disease progression after completion of prior treatment to death (primary analysis)
- Time from first implantation to death (secondary analysis)
- Time from diagnosis of Stage IV disease to death (secondary analysis)

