10.1 Efficacy Outcomes

10.1.1 All-cause mortality

All-cause mortality for primary analysis is defined as time from date of the first scan showing disease progression after completion of prior treatment (time of origin, T_0) to death from any cause. Subjects still alive at the time of analysis will be censored at that time point.

Secondary analyses of time from first implantation to death, and time from diagnosis of Stage IV disease to death, will be analyzed similarly.

For all time-to-death analyses the Kaplan-Meier curves will be presented; respective 95% two-sided confidence intervals (CIs) will be calculated.

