11.1 Safety Outcomes

11.1.1 Subject disposition

Subject disposition will be recorded at the EOS visit (120 days after the last implant) or at time of patient death or withdrawal, whichever occurs first.

Reasons why surviving patients received < 4 implants will be summarized. These reasons can include patient request (voluntary withdrawal), AE, protocol violation, request of Investigator or Regulatory Authority, request of Sponsor, lost to follow-up or other. One reason will be specified per patient.

Dates of Screening, date of the first scan showing disease progression after completion of prior treatment and the date of each implant will be listed.

Number and percentage of patients receiving 1, 2, 3 or 4 implants will be summarized. For all patients who received at least one implant, the number of days on study after each implantation will be summarized.

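### The SAP's only table and only origin-labelled figure for the primary outcome start survival at the most recent progression scan instead of the first; Amendment 11 and the SAP also name different pancreatic primaries

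*SAP*

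**What the plan says.** **Origin of the primary outcome, SAP text.** Every operative definition points to the first scan.
- SAP 3.3.1: "The primary efficacy outcome is post-implantation all-cause mortality, where time to death is defined as the time from the first scan showing disease progression".
- SAP 6.4.1: "Time from first scan showing disease progression after completion of prior treatment to death (primary analysis".
- SAP 10.1.1: "All-cause mortality for primary analysis is defined as time from date of the first scan showing disease progression after completion of prior treatment".
- SAP List of Definitions, on T0: "Scan must be prior to first implant. Used for mortality analyses only".
- SAP 11.1.1 lists the matching date: "date of the first scan showing disease progression after completion of prior treatment and the date of each implant will be listed".
- Listing 16.2.6.4.1 in SAP 16.1 agrees: "Overall survival (from T ₀".

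**Origin of the primary outcome, SAP output list.** In SAP 16.2, Table 14.2.4 is "Overall survival (from the most recent radiological scan showing evident disease progression to death" and Mortality Figure 16.2.6.4.1 is "Overall survival (from the most recent radiological scan showing progression". Figures 14.2.1.2.1 and 14.2.1.2.X in SAP 16.3 are called Overall Survival and give no origin. One bullet of SAP 10.2 plots survival against time counted from implantation.

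**Pancreatic primary.** Protocol Amendment 11 (synopsis and 3.2.1) makes Response Rate the primary objective and puts overall survival among the secondary objectives (3.2.2). It adopts the SAP's outcomes under the colorectal heading only (3.1). Its Appendix 3, item 6, takes the primary objectives from protocol Section 3 and leaves their analysis to the SAP. The SAP cites Amendment 10 (SAP 2) and plans 30 implanted patients (SAP 3.2). It makes all-cause mortality primary with no exception for the pancreatic cohort (3.3.1, 10).

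**The concern.** A table shell is what gets programmed and what reaches the study report. Here the shell for the headline result names a different starting point from the definition it is meant to serve, and the matching figure makes the same substitution. Tables 14.2.5 and 14.2.6 belong to the two secondary survival outcomes, so no listed table carries the primary outcome as defined.

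For the pancreatic cohort the two documents disagree on which result is the headline. Survival is reported for these patients either way, so what is at issue is which result counts as primary and how a response rate would be produced.

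All analyses are declared exploratory (SAP 6.2), so no type I error rate is at risk. What is at risk is the headline estimate and its use: SAP 3.2 and protocol 7.1 both say the results feed the planning of later trials.

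**Working it through.** The plan states no figure for this point, so there is nothing to reproduce. The check compares the texts and then works out the direction of the shift.

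**Step 1. Outputs that could carry the primary outcome.**
- Tables: one (14.2.4), origin at the most recent scan.
- Figures with a stated origin: one (Mortality Figure 16.2.6.4.1), origin at the most recent scan.
- Figures without an origin: two entries (14.2.1.2.1 and 14.2.1.2.X).
- Listings: one (16.2.6.4.1), origin T0.

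The listing and the mortality figure share a number but not an origin.

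**Step 2. Direction of the shift.** For one patient, let F be the date of the first qualifying scan (T0), R the date of the most recent progression scan, I the date of the first implant, and D the date of death or censoring.
- Survival as defined = D − F.
- Survival as titled = D − R.
- Defined minus titled = R − F, which is at least 0.

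Three cases follow:
- One qualifying scan: R = F, and the difference is 0.
- Two or more scans on different dates, all before implant: F < R ≤ I. The difference is positive and at most I − F. The documents set no limit on I − F.
- Most recent scan after implant, which the titles do not rule out: R > I. The difference is larger than I − F. Titled survival is then shorter than D − I, the secondary outcome timed from first implantation.

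**Step 3. Size.** Neither document gives scan dates, a distribution of R − F, or an assumed survival time. The average or median shift cannot be derived.

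**Step 4. Pancreatic cohort.**
- Amendment 11, Appendix 3, item 9: 40 of 74 patients; 40/74 = 54.1%.
- SAP 3.2: 10 of 30 patients; 10/30 = 33.3%.

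These are cohort shares, not effects.

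**Step 5. What exists for Response Rate.** Protocol 3.2.1 lists five items and does not say how, or whether, they combine. Protocol 7.2 describes an evaluation team, the timing of review, a single baseline, a response table and a rating scale. SAP 10.1.3 defines a tumor marker response as a fall of at least 20% in CEA, CA 19-9 or both, and SAP 10.2 gives exact 95% intervals for rates. The SAP does not take up protocol 7.2, gives no overall responder rule, and lists no Response Rate table.

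**The case against.** **It is only a title slip.** The definitions are consistent, the first-scan date is the one listed, and an analyst who followed SAP 10.1.1 would get the right answer. The same appendices hold other label slips: CA 19-9 for colorectal patients is titled twice, and the threshold for frequent events is 2% in Table 14.3.1.6 but 10% in SAP 11.1.2. This stands as far as it places the error in the output specifications. It does not remove the error. Two outputs carry the same alternative origin, they are the ones for the primary outcome, and nothing says that text prevails over titles.

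**The SAP already settles the pancreatic primary.** It says that it supersedes the protocol's statistical considerations, that response rate was deliberately modified because tumor measurements often cannot be obtained, and that differences will be explained in the clinical study report. This explains the mismatch. It does not resolve it, because the SAP was written for Amendment 10 while Amendment 11 still states Response Rate. An explanation at reporting does not fix the primary in advance. The SAP's own date is not in the text supplied, so its order relative to Amendment 11 rests on the version it cites.

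**Stronger readings that the documents do not support.**
- A reader might infer that Kaplan-Meier curves are planned only from implantation. SAP 10.1.1 plans them for all time-to-death analyses, and another bullet of SAP 10.2 plans them from the primary origin, if feasible. Only one bullet is at fault.
- A reader might infer that Response Rate has no planned analysis at all. Protocol 7.2 and the SAP elements in step 5 show otherwise; what is missing is their completion in the SAP.
- A reader might infer that Table 14.2.4 would lie within 21 days of Table 14.2.5, because protocol 5.1.1 places baseline PET-CT or MRI within 21 days before implant. That borrows a pre-implant rule the titles lack. Protocol 5.1.1 also allows individual exceptions to pretreatment timing, and entry progression may be shown by tumor markers (4.3.1, item 5). The number of patients it would cover is unknown.

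**Conclusion.** The first part is wrong as written. The primary outcome's only table and only origin-labelled figure specify a different origin from the SAP's own definition and omit the pre-implant limit. If both scans precede implant, the titled survival is never longer than survival from T0 and equals it only for patients with one qualifying scan. A post-implant scan would shorten it further. The direction follows from the definitions alone; the size cannot be derived, and any figure in months would rest wholly on assumed scan dates.

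The second part is a secondary point of document alignment. Amendment 11 and the SAP name different pancreatic primaries, for 40 of 74 planned patients under Amendment 11, and the SAP does not complete the Response Rate analysis that Amendment 11 refers to it.

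A conditional gap follows. T0 requires prior treatment, and protocol 4.3.1, item 4, lets pancreatic patients enter without prior chemotherapy. T0 is therefore undefined for any who had no prior treatment of any kind. The documents do not say whether there will be such patients, and SAP 3.2 describes a population in whom standard therapy has failed.

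**What to change.** - Retitle Table 14.2.4 and Mortality Figure 16.2.6.4.1 to *Overall survival from T0 (first progression scan after prior treatment ended, taken before the first implant)*.
- State the origin in Figures 14.2.1.2.1 and 14.2.1.2.X.
- Amend the SAP 10.2 bullet so that each time-to-death plot uses the origin that SAP 6.4.1 gives for that analysis.
- Issue a SAP version tied to Amendment 11 that names one primary outcome for the pancreatic cohort. Which one is the sponsor's choice.
  - If Response Rate: carry protocol 7.2 into the SAP, with a responder rule and a table.
  - If mortality: align protocol 3.2.1 and the synopsis, and define T0 for any pancreatic patient with no prior treatment.

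The cost is a short SAP revision with no new data. Under protocol 8.6, written IRB and FDA approval is needed only if protocol text changes.

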16.3 Figures

Figure #	Figure
14.2.1.1.1.1	Progression-Free Survival: any death
14.2.1.1.1.2	Progression-Free Survival: cancer-related death
14.2.1.1.X	Progression-Free Survival by Stratifier X
14.2.1.2.1	Overall Survival
14.2.1.2.X	Overall Survival by Stratifier X
14.2.1.3.1	Radiographically-evident PFS
14.2.1.3.X	Radiographically-evident PFS by Stratifier X
14.2.2.1.1	CA125, colorectal
14.2.2.1.2	CA125, pancreatic
14.2.2.2.1	Tumor markers, CA 19-9, colorectal
14.2.2.2.2	Tumor markers, CA 19-9, colorectal
14.2.2.3.1	Tumor markers, CEA, colorectal
14.2.2.3.2	Tumor markers, CEA, pancreatic
14.2.3.1.1	Chemistry, C-reactive protein, colorectal
14.2.3.1.2	Chemistry, C-reactive protein, pancreatic
14.2.4.1.1	Hematology, Sedimentation rate, colorectal
14.2.4.1.2	Hematology, Sedimentation rate, pancreatic

End of Analysis Plan
